11.4.5.3 Adverse events

Adverse events will be graded according to the NCI CTCAE v4.03 (and classified by SOC/PT) according to the latest available version of the Medical Dictionary for Regulatory Activities (MedDRA) dictionary.

Adverse event observation period

- Pretreatment AEs are defined as any AE reported during the screening period.
- TEAEs are AEs that developed or worsened or became serious during the treatment period.
- Posttreatment AEs are AEs that developed or worsened or became serious during the posttreatment period.

The grade will be taken into account in the summary. For patients with multiple occurrences of the same PT, the maximum grade will be used.

The primary focus of AE reporting will be the TEAEs. Posttreatment AEs will be described separately.

Treatment-emergent adverse events will be summarized with the number and percentage of patients with AEs, classified by MedDRA PT and intensity as graded by the NCI CTCAE v4.03.

Adverse event incidence tables will present the number (n) and percentage (%) of patients experiencing an AE by primary SOC, high level group term (HLGT), high level term (HLT), and PT, sorted by the SOC internationally agreed order. The other levels (HLGT, HLT, and PT) will be presented in alphabetic order.

The following TEAE summaries will be generated for the all treated population:

- Overview of TEAEs, summarizing number (%) of patients with any:
 - TEAE,
 - Grade ≥ 3 TEAE,
 - Grade 3 to 4 TEAE,
 - Grade 5 TEAE (any TEAE with a fatal outcome during the treatment period),
 - Serious TEAE,
 - TEAE leading to treatment discontinuation.
- In addition, an overview of Grade 5 AEs will be provided summarizing number (%) of patients with any:
 - Grade 5 AE (TEAE and posttreatment),
 - Fatal TEAE,
 - Grade 5 TEAE (TEAE with a fatal outcome during the treatment period),
 - Any grade TEAE with a fatal outcome during the posttreatment period,

- Posttreatment Grade 5 AE (excluding a TEAE that worsened to Grade 5 during the posttreatment period).

11.4.5.4 Deaths

The following summaries of deaths will be generated:

- Number (%) of patients who died by study period (screening, treatment, posttreatment) and reasons for death (disease progression, AE, or other reason).
- Deaths in nonenrolled patients or enrolled but not treated patients.
- All TEAEs leading to death by primary SOC and PT showing number (%) of patients.

11.4.5.5 Analyses of laboratory safety variables

Clinical laboratory values will be analyzed after conversion into standard international units. Clinical laboratory parameters will be graded according to the NCI CTCAE v4.03 scale, when applicable, and analyzed according to the out-of-normal laboratory range value, when the NCI CTCAE scale is not applicable.

The number of patients with abnormal laboratory tests at baseline (Grade ≥ 1) will be presented by grade. The frequency of patients in each grade of laboratory test during treatment will be summarized. For patients with multiple occurrences of the same laboratory variable during the on-treatment period, the maximum grade (worst) per patient will be used. The denominator used for the percentage calculation is the number of patients with at least 1 evaluation of the laboratory test during the considered observation period.

When the NCI CTCAE v4.03 scale is not applicable, the number of patients with a treatment-emergent out-of-normal laboratory range value will be displayed.

11.4.5.6 Analyses of vital signs variables

For blood pressure (systolic, diastolic), temperature, weight, and BSA, a descriptive table will be provided with the last and worst (highest and lowest) evaluations: raw data and changes from baseline.

For ECOG PS, a shift table reporting the last and worst evaluations respective to baseline will be provided.

11.4.5.7 Immunogenicity

Analyses will be performed on the evaluable population for immunogenicity.

The immunogenicity for SAR566658 will be assessed by summarizing the number and the percentage of patients with ATA positive or negative status at baseline. In addition, ATA titers will be summarized using descriptive statistics by dose level.

11.4.5.8 Analyses of other safety variables

Number (%) of patients with an ECG abnormality at baseline and/or at any postbaseline time points will be presented according to the baseline status.

11.4.6 Analyses of pharmacokinetic variables

Plasma concentrations of SAR566658, naked huDS6 (SAR404461) and unconjugated maytansinoids (DM4 and Me-DM4) will be summarized using arithmetic and geometric means, standard deviation, standard error of the mean, coefficient of variation, minimum, median, and maximum by theoretical sampling time (PXX). Allowed time windows will be specified in a separate document.

Plasma concentrations of SAR566658, naked huDS6 (SAR404461) and unconjugated maytansinoids (DM4 and Me-DM4) will be used for population PK analysis using a nonlinear mixed-effects modelling approach. Additional details of the analysis plan will be provided in a separate document. This analysis will involve an estimation of interpatient PK variability, population PK parameter estimates, and the assessments of patho-physiologic covariate effects on clearance and possibly on volume, if warranted. Empirical Bayesian estimation of individual PK model parameters and of individual exposure parameters of interest (such as C_{max} and AUC) will also be performed. Those estimates will then be investigated as prognostic factors for clinical outcome including safety and efficacy endpoints, if possible.

Previous PK data collected in other clinical studies such as TED10499, in which intensive blood sampling protocols were used, may be considered to help in model building.

Full details of the analyses of PK variables will be reported in a standalone population PK report.

11.4.7 Exploratory analyses on biomarkers

11.4.7.1 Predictive markers of response

[REDACTED] Analyses will be performed to explore the relationship between these markers and treatment efficacy (ORR, tumor shrinkage) in the all treated population.

Covariates as number of prior lines will be taken into consideration in interpreting the treatment efficacy observed in the all treated population.

Further analyses will be described in the SAP.

11.4.7.2 Pharmacodynamics biomarkers on posttreatment samples

[REDACTED]
Further analyses will be described in the SAP.

11.5 INTERIM ANALYSIS

Interim analyses of efficacy, safety, and other data will be performed after 14 patients are treated at each dose level at the end of Part 1. These interim analyses are planned to occur when all patients have completed at least 4 postbaseline tumor assessments, experienced confirmed objective response, or discontinued the study for any reason. However, if the futility criteria of 2 responders is either met or not met with certainty for both arms when all patients have completed 2 postbaseline tumor assessments, experienced confirmed objective response, or discontinued the study for any reason, the analyses may be conducted at that time instead. Enrollment will be interrupted after completion of enrollment in Part 1, until completion of the Part 1 interim analysis.

An interim analysis based on efficacy will be performed to assess futility (to reject early the hypothesis that the response rate is 30%). If there is 0 or 1 response (CR or PR) in the first 14 patients treated at each dose, the 7.1% critical boundary is not met and the alternative hypothesis of at least 30% will be rejected. If the critical boundary of 7.1% is reached (2 responses or more), the study can continue in Part 2 at the selected dose.

At the same interim analysis, overwhelming efficacy will be assessed (to reject early that the response rate is less than or equal to 12%). If there are 6 responses or more in the first 14 patients treated at 1 dose, the critical boundary of 42.9% (1-sided nominal significance level of 1.8%) is reached and the null hypothesis of 12% will be rejected.

Overall, this procedure has 80% statistical power (1-sided alpha level of 10%) to reject the null hypothesis, using a gamma (-2) beta spending function for futility analysis and a Lan-DeMets (OF) alpha spending function in a 1 sample test for a binomial proportion (East version 6.3 using exact computations, Cytel Software, Cambridge, MA).

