6.2.2 Determination of end of clinical trial (all patients)

The first cut-off date for the selection of the selected dose corresponds to the date on which all patients treated in Part 1 (whatever the dose) have had at least 4 postbaseline tumor assessments, experienced confirmed objective response, or have discontinued the study for any reason. However, if the futility criteria of 2 responders is either met or not met with certainty for both arms when all patients have had 2 postbaseline tumor assessments, experienced confirmed objective response, or discontinued the study for any reason, the first cut-off date may be done at that time instead. The recruitment will be put on hold at the time of the interim analysis until the decision regarding dose selection and the start of Part 2 has been made. The recruitment will be authorized in Part 2 only when the selected dose is chosen.

The second cut-off date for primary ORR analysis corresponds to the date on which all patients treated in Part 2a and Part 2b have had at least 4 postbaseline tumor assessments, experienced confirmed objective response, or have discontinued the study for any reason. However, if the primary criteria of 7 responders is either met or not met with certainty at the end of the Part 2a in the selected dose when all patients have had 2 postbaseline tumor assessments, experienced confirmed objective response, or discontinued the study for any reason and when all the patients of the Part 2b have had 2 postbaseline tumor assessments, experienced confirmed objective response, or discontinued the study for any reason, the second cut-off date may be done at that time instead.

If a patient continues to benefit from the treatment after the second study cut-off, the patient can continue study treatment until disease progression, unacceptable toxicity, or patient's refusal of further study treatment, and will continue to undergo all assessments as per the study flow chart.

Patients without documented disease progression but not on treatment at the second cut-off date will be followed for any ongoing AEs. In addition, imaging to document disease progression and survival status will be collected (every 6 weeks) for 6 months after the cut-off date.

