6.3 INTERIM ANALYSIS

Interim analyses of efficacy, safety, and other data will be performed after 14 patients are treated at each dose level at the end of the Part 1. Further statistical details are provided in [Section 11.5](#).

A preliminary statistical evaluation of antitumor activity by RECIST 1.1 will be done on the first 14 patients treated in each cohort; if at least 2 confirmed responses (PR or CR) in at least 1 cohort are observed then the study can continue in Part 2, if the safety profile is acceptable.

In addition to the efficacy criteria, safety criteria including the number (%) of patients experiencing an eye disorder leading to dose modification or drug discontinuation, or peripheral neuropathy, or a treatment-emergent adverse event (TEAE) leading to dose reduction or drug discontinuation, will be considered.

In case of the efficacy criteria (<2 PR or CR in 14 patients) not being reached for a given dose, then this dose will not be selected.

In case of neither dose reaching the efficacy criteria (<2 PR or CR in 14 patients), then the study will be stopped.

In case of comparable ORR and safety profiles between 90 mg/m² D1D8 q3w and 120 mg/m² D1D8 q3w, then the lower dose (90 mg/m² D1D8 q3w) will be chosen.

In case of a higher ORR in 120 mg/m² D1D8 q3w and a comparable safety profile to 90 mg/m² D1D8 q3w, then 120 mg/m² D1D8 q3w will be chosen.

In case of a higher ORR in 120 mg/m² D1D8 q3w and a better safety profile with 90 mg/m² D1D8 q3w, then the dose will be selected on the best risk/benefit.

If there are 6 responses or more in the first 14 patients treated at 1 dose, then the study could be stopped for overwhelming efficacy.

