11.1.2 Sample size determination for the mild CA6 expression cohort (Part 2b)

At the selected dose, the relationship between CA6 expression level and efficacy outcome will be assessed by adding a cohort of 20 patients with mild CA6 membrane staining (at least 1% positive tumor cells at intensity $\geq 1+$ and $< 30\%$ of tumor cells at intensity 2+, 3+).

With a sample size of 20 patients, a true response rate above 15% can be rejected with 83% confidence if we observe 0 or 1 response. Moreover, if we observe 7 responses over the 29 patients in the biomarker positive group ($\geq 30\%$, 2+,3+) and ≤ 1 response in the mild CA6 biomarker positive group (CA6 IHC = $< 30\%$ 2+,3+ and $\geq 1\%$, $\geq 1+$), the 1-sided p-value (according to Fisher's exact test) will be around 7%, suggesting an association between biomarker status and ORR.

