2.1.3 Efficacy endpoints

2.1.3.1 Primary efficacy endpoint(s)

The primary efficacy endpoint will be the Overall Response Rate (ORR) defined as the proportion of patients with confirmed complete response (CR) or confirmed partial response (PR) as Best

Overall Response (BOR), assessed by the Investigator (based on RECIST 1.1), relative to the total number of patients in the efficacy population (see [Section 2.3.1](#)). Confirmation of objective responses will be performed by repeat tumor imaging (Computed Tomography [CT] scan, MRI) at least 4 weeks after the first radiological documentation of response.

Tumor assessments will be performed every 6 weeks (ie, every 2 cycles) during the treatment period and every 6 weeks during the follow-up period if a patient discontinues treatment prior to radiologic disease progression.

Tumor assessments after the initiation of post-treatment anti-cancer therapy will be excluded from the determination of Best Overall Response in a patient. See [Appendix B](#) (Determination of tumor response) for details.

Best Overall Response

BOR is the best tumor response observed from first study treatment infusion until disease progression, death or initiation of post-treatment anti-cancer therapy, whichever occurs first.

Primary ORR analysis can be performed when all patients treated in Part 2a and Part 2b have had at least 4 postbaseline tumor assessments, experienced confirmed objective response, or have discontinued the study for any reason. However, if the primary criteria of 7 responders is either met or not met with certainty at the end of the Part 2a in the selected dose when all patients have had 2 postbaseline tumor assessments, experienced confirmed objective response, or discontinued the study for any reason and when all the patients of the Part 2b have had 2 postbaseline tumor assessments, experienced confirmed objective response, or discontinued the study for any reason, analysis may be done at that time instead.

Best tumor shrinkage

For patients with measurable disease, the best tumor shrinkage will be defined by the best relative change from baseline as follows:

$$Y = 100 \times \frac{Y_{smallest} - Y_{baseline}}{Y_{baseline}}$$

Where Y is the sum of longest diameter of the target lesions.

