2.4.4 Analyses of efficacy endpoints

2.4.4.1 Analysis of primary efficacy endpoint(s)

Response rate will be analyzed based on all-treated population as defined in the [Section 2.3.1.1](#).

Overall Response rates will be summarized using counts (n) and percentages (%) and presented with its 2-sided 80% confidence interval using the Clopper and Pearson exact method.

At the end of the Part 2a in the overexpression cohort at the selected dose, an exact binomial test of the null hypothesis that the true response rate is 12% will be performed using a one-sided 0.1 alpha level.

Best Overall Response (BOR) (CR, PR, SD, PD, and NE) will be summarized using counts (n) and percentages by treatment group. At the end of the part1, a summary of BOR by intended dose levels and ECOG stratification factor will also be provided.

For responder patients, a listing with number of prior advanced regimen, prior treatment with anthracycline and/or taxanes (yes/no), prior treatment with eribulin (yes/no), best response to last advanced previous anti therapy, baseline CA6 IHC, baseline circulating CA6, best overall response to SAR566658, duration of response and reason for treatment discontinuation will be provided.

Exploratory analyses

At the end of the Part 2a in the overexpression cohort, ORR will be estimated (with its 80% CI) in several subgroups of patients defined in the table below. A forest plot with estimation of ORR in each subgroup will be provided, if enough patients in each stratum. Depending upon the study results, additional subgroups may be examined, and subgroups with small sample sizes may be pooled to create a larger meaningful subgroup.

Table 3 – Subgroup analyses

Prognostic factor	Description
Age	[18-65[y, [65-75[y, ≥75y
ECOG PS at baseline	0, 1
Any prior eribulin agent	Yes vs No
Mutation BRCA1	Yes vs No
Mutation BRCA2	Yes vs No
Number of organs involved	1,2 ≥3
Number of prior regimen	1,2,3
Bone metastasis only vs visceral metastasis	Yes vs No
DFS	≤24 mo vs >24mo
PD1	Classes to be defined
PDL1	Classes to be defined

Sensitivity analyses of the primary efficacy endpoint

The ORR will also be estimated on the response-evaluable population as defined in [Section 2.3.1.2](#). Depending on the results, exploratory analyses as defined in the [Table 3](#) may also be performed on the response-evaluable population.

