4 DATABASE LOCK

The database is planned to be locked when all patients have completed at least 4 postbaseline tumor assessments, experienced confirmed objective response, or discontinued the study for any reason.

In case of early discontinuation of the study (for futility for instance), the database lock can be performed when all patients have completed at least 2 postbaseline tumor assessments, experienced confirmed objective response, or discontinued the study for any reason.

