Appendix B Determination of tumor response

The overall response at each time point and the best overall response will be determined by the Investigator derived from the tumor measurements data according to RECIST 1.1 criteria ([Appendix C](#)) using the following algorithm.

- Overall Response:

Overall response, or integrated response, will be determined by the investigator using assessments of target, non-target and new lesions according to RECIST 1.1. See [Appendix C](#) for details.

- Confirmation:

According to RECIST 1.1 a confirmed CR or PR will be based on two tumor assessments at least four weeks apart as follows: if a CR or PR outcome is reported, then a second tumor assessment with CR or PR at least four weeks later is needed for confirmation, regardless of how many “unknown/not applicable/missing/non evaluable” tumor assessments are in between the two outcomes.

- Best Overall Response (BOR) :

In general, a patient’s best tumor response will depend on the achievement of both: documented tumor measurement assessments and confirmation of the tumor response by RECIST1.1 criteria. For each patient the BOR will be derived based on the following algorithm:

– a) PR/CR will be determined based on confirmed PR and confirmed CR described in the algorithm above.

– b) SD and PD will be determined from the overall tumor response at each timepoint. If SD is the overall response and it occurs less than 35 days from first study administration, then overall response will not be SD. For patients who stop the treatment due to a symptomatic deterioration or death, without any other tumor assessment before the symptomatic deterioration or death, then the BOR will be considered as NE. These cases will be described separately as patients in early progression or early death.

If PD is the overall response and it occurs less than 42 days from the first study administration, then the best overall response is PD.

– c) Convention for PD after several NE cycles: in the case where the assessment at study entry is followed by several visits (or cycles) with no assessment (or only NE assessments or SD <35 days from first study administration) for more than twice the periodicity of tumor assessments (ie, for more than 42 days), and the next assessment is PD, the best overall response will be NE. If the PD occurs within this period of time, the best overall response will be PD.

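### The optional two-scan cut-off settles only the 2-responder or 7-responder count, so responses awaiting confirmation can drop out of the dose comparison, the 6/14 check and the Part 2a and Part 2b ORR estimates

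*Protocol*

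**What the plan says.** **Default and option.** The Part 1 analysis waits until every patient has four post-baseline scans, a confirmed response, or has left the study (Protocol synopsis, 6.2.2 and 11.5; SAP 3). It may be brought forward "if the futility criteria of 2 responders is either met or not met with certainty for both arms when all patients have completed 2" scans. The second cut-off, for the primary ORR analysis, has a parallel option. If the 7-responder criterion in Part 2a is settled with certainty at two scans, and "when all the patients of the Part 2b have had 2 postbaseline tumor assessments" (or a confirmed response, or discontinuation), then "the second cut-off date may be done at that time instead". Nothing further is required of Part 2b.

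**Confirmation.** Scans are 6-weekly (SAP 2.1.3.1). Once a CR or PR is reported, "then a second tumor assessment with CR or PR at least four weeks later is needed for confirmation" (SAP Appendix B).

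**Uses of ORR beyond the two thresholds.**
- Dose selection compares the arms. Protocol 6.3 and SAP 1.1 have one rule beginning "In case of comparable ORR and safety profiles between 90" and others for a higher ORR at 120 mg/m², all read together with safety.
- Six or more responses in 14 may stop the study for efficacy (Protocol 11.5, SAP 3).
- ORR is "presented with its 2-sided 80% confidence interval using the Clopper and Pearson exact method" (SAP 2.4.4.1), and the expression cohorts are compared with a 1-sided Fisher test (SAP 2.4.6.2).

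**Lock.** SAP 4 plans the lock at four scans. It adds: "In case of early discontinuation of the study (for futility for instance), the database lock can be performed when all patients have completed" two.

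**The concern.** The certainty wording guards the two go/no-go counts, but ORR does other work at the same data cut. In Part 1, when both arms have reached 2/14, the futility criterion no longer separates the doses and their relative ORR becomes one of the inputs to selection. That is also a situation in which the early option opens. In Part 2b, ORR is the primary endpoint and the option asks only for two scans. A recent enrolee with an unconfirmed PR at the second scan counts as a non-responder in all these analyses.

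The error runs one way, since leaving out pending responses can only lower confirmed ORR. At stake are a blurred or occasionally reordered dose comparison, a missed 6/14 signal, and downward-biased estimates in Parts 2a and 2b.

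**Working it through.** **1. The plan's own figures.** The two-stage exact sum is P(X₁≥6) + Σ P(X₁=x)·P(X₂≥7−x) over x = 2 to 5, with n₁=14 and n₂=15. It gives 80.0% power at 30% (stated 80%) and attained alpha 5.0% at 12% (limit 10%). For Part 2b, P(X≤1 | 20, 15%) = 0.176, so confidence is 82.4% (stated 83%). 1-sided Fisher for 7/29 vs 1/20 is 0.079 (stated around 7%). None of this depends on the cut-off date, and the fix leaves the design unchanged.

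**2. Who is affected.** Scan 2 falls at 2 × 42 = 84 days. A response first seen there cannot be confirmed before 84 + 28 = 112 days. If a patient enrolled g weeks before the last one, first response is at week s and confirmation takes c weeks, the response counts at the early cut-off only if s + c ≤ 12 + g:
- Scan 1 (s = 6), c = 4 or 6: always counted.
- Scan 2 (s = 12): needs g ≥ c, that is 4 or 6 weeks.
- Scan 3 (s = 18): needs g ≥ 6 + c, that is 10 or 12 weeks.

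So only recent enrolments are exposed.

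**3. Assumptions.** The documents give neither time to response nor accrual. Assumed: first response at scans 1/2/3 in 70/20/10% to 40/35/25%; confirmation at 4 or 6 weeks; uniform entry over 24 to 40 weeks. Protocol 4.2 puts overexpression at 29 to 35%, so 28 patients need about 28/0.35 = 80 to 28/0.29 = 97 prescreened. That suggests accrual is not instant but gives no calendar time.

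**4. Share missing, by hand.** With accrual over A weeks, the share is about f₂·c/A + f₃·(6+c)/A, where f₂ and f₃ are the proportions first responding at scans 2 and 3.
- Low: 0.20 × 4/40 + 0.10 × 10/40 = 4.5%.
- High: 0.35 × 6/24 + 0.25 × 12/24 = 21.3%.

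**5. Part 1 simulation.** 40,000 trials per scenario, blocks of four, true ORR 15% vs 30% or 30% vs 30%, conditional on at least 2 confirmed in both arms at the early cut-off (42 to 88% of trials). The comparator is all responses first seen by scan 3 and confirmed.

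| | Early cut-off | With the fix |
|---|---|---|
| Eventual responses missing | 5–21% | 1.5–6.5% |
| Change in whether 120 mg/m² is strictly higher | 6–20% | 2–8% |
| Full reversal of ordering | 0.3–5% | below 1% |

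**6. Part 2b at true ORR 15%.** Applying step 4, 15% × (1 − 0.045) = 14.3% and 15% × (1 − 0.213) = 11.8%. Simulation (100,000 trials per scenario, 20 of 35 Part 2 patients) gives a mean of about 11.6 to 14.3%, with at least one response missing in 15 to 50% of trials. With the fix the mean is 14.0 to 14.7%.

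The exact 80% interval lies wholly below 15% only at 0/20 (upper limit 10.9%; at 1/20 it is 18.1%). That chance is 0.85²⁰ = 3.9% with complete data and about 5 to 9% at the early cut-off.

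**7. One pending response, as an example.** 1/20 (80% CI 0.5–18.1%) becomes 2/20 (2.7–24.5%). Fisher p moves from 0.079 (7/29 vs 1/20) to 0.191, 0.126 or 0.080 for 7/29, 8/29 or 9/29 vs 2/20, since Part 2a can have pending responses too.

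**8. Faster accrual.** Over 12 weeks the figures are worse: up to about 36% of Part 1 responses missing, reversals up to about 11%, Part 2b mean 8.5 to 12.6%, and a 7 to 17% chance that the interval misses 15% from below.

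**The case against.** **The option is a permission.** The study is open-label, response is investigator-assessed, and the Steering Committee reviews interim ORR, so pending responses would be visible and the sponsor could wait. This stands: every size above is conditional on the option being used. The Part 2b figures are also not conditioned on the 7/29 criterion being settled, so they describe trials in which the option is available and taken. Still, nothing in the text requires anyone to wait.

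**A reader might infer that the wrong dose would be chosen.** The documents do not support that. The plan has no strictly-higher rule; it speaks of comparable or higher ORR alongside safety, risk/benefit and PK. Most ordering changes in step 5 create or break ties.

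**A reader might infer a wrong test decision.** The 2/14 and 7/29 decisions are protected by the certainty wording. For Part 2b, the sentence that "a true response rate above 15% can be rejected with 83% confidence if we observe 0 or 1 response" (Protocol 11.1.2) illustrates the sample size and is not a decision rule. An exact two-sided 80% interval allows up to 10% error per tail, and 5 to 9% is inside that; only the 12-week case can exceed it.

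**A reader might infer that the SAP leaves open which ORR is primary.** It does not. Protocol 6.2.2 and SAP 2.1.3.1 attach the primary analysis to the second cut-off, early or not. SAP 2.1.3.1 concerns analysis timing and SAP 4 lock timing, so this is an ambiguity and not a contradiction. What stays open is whether a two-scan analysis can precede the planned four-scan lock when the study continues, and whether ORR is then updated.

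**Conclusion.** The point holds as a gap in the early cut-off condition. The trigger secures 2/14 and 7/29 and leaves four things exposed: the between-dose comparison when both arms have at least 2 responders; the 6/14 check; the Part 2a ORR and its interval; and the Part 2b ORR, its interval and the Fisher comparison. The direction is certain. The size rests on assumed accrual and response timing and on the option being used.

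Over 24 to 40 weeks of accrual the loss of Part 1 responses is modest to material and full reversals are uncommon. In Part 2b the harm is a biased estimate, about 0.7 to 3.4 percentage points low at a true 15% (15 − 14.3 and 15 − 11.6), in a cohort with no formal decision rule. This is a cheap improvement worth making; it does not undermine the design.

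**What to change.** Add one sentence to the Protocol synopsis, 6.2.2 and 11.5 and to SAP 2.1.3.1 and 3: the early cut-off may be used only after every CR or PR already seen at the two-scan date, in the cohorts being analysed (both Part 1 arms; Part 2a and Part 2b), has had its confirmatory scan or can no longer be confirmed.

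Add one sentence to SAP 4 aligning it with 2.1.3.1: say whether a two-scan primary ORR analysis can be run when the study is not stopped early, and whether ORR is updated at the later lock.

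**Cost.** Sample size, thresholds, power and alpha do not change. When a confirmation is pending, the median wait is about 2.5 to 4.2 weeks and the maximum about 4 to 6 weeks, which lengthens the Part 1 recruitment hold. The remedy is partial, because responses first appearing at scan 3 or later can still be missed.
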